4. At least 3 months post-amputation per physician discretion
5. Residual limb length greater than 6.5 inches in length
6. Able to follow directions and give informed consent on their own or through Legally Authorized Representative.
7. Must be able to ambulate without assistance. An external assistance device such as cane or walker will be permitted.
8. Adequate arterial blood flow of the index stump as evidenced by TcOM > 30 mmHG, measured within the past 12 months.

IV. Exclusion Criteria:

1. Conditions that prevent wearing a prosthetic socket; such as existing scab, ulcer, or keloid scar on amputation stump.
2. Cognitive deficits or mental health problems that would limit ability to consent and participate fully in the study protocol
3. Women who are pregnant or who plan to become pregnant in the near future

V. Study Design:

This study has 3 aims where trans-femoral and trans-tibial amputees will be enrolled.

Subjects enrolled in Aim 1 (N=20) will have one study visit that will take place at The Ohio Willow Wood (OWW).

Subjects enrolled in Aim 2 (N=30) will have a total of 4 visits at baseline, month 1, month 2, and month 3.

Subjects in Aim 3 (120) will be enrolled at Indiana University (n=30 subjects), OWW (n=30), and at Walter Reed National Military Medical Center (WRNMMC) (n=60 subjects) with a total of 3 visits at 0 week (baseline), 0-4 weeks (socket fitting visits), and 16 weeks (final visit).. OWW and Walter Reed National Military Medical Center (WRNMMC) have separate IRB protocol & approval to conduct their part of subject recruitment and study visits. Aims 2 and 3 will not be run concurrently. Subjects enrolled in Aim 2 can participate in Aim 3. Aim 2 studies performed at Ohio State and Indiana University. Aim 2 has enrolled 15 subjects through Ohio State University & OWW (and these 20 subjects have completed their participation in the study) and the data is currently being analyzed to determine if additional subjects are required. If analysis shows sufficient subjects have been enrolled to achieve the study aim, no additional subjects will be enrolled in Aim 2. If there is insufficient data, the remainder of the Aim 2 subjects will be enrolled through OWW under their approved IRB with WIRB. Aim 3 studies performed at IU, OWW and WRNMMC per their approved IRB protocols. The vacuum suspension used for the study is new to all enrolled subjects

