- Hitachi Aloka Ultrasound – A hand held device will be moved gently across the skin and measure your blood flow of deeper skin tissues.
- Skin Temperature-A small tab (small sticker) will be placed on the skin and tell us the temperature of your residual limb
- Surface Electrical Capacitance – Small non-invasive probe place on skin to measure skin hydration
- Trans epidermal water loss measurement (TEWL) – Small non-invasive probe compares relative humidity of skin surface to indicate epidermal barrier function
- Transcutaneous Oxygen Measurement – Small non-invasive probe measures the amount of oxygen released through the skin layer
- This data will be used to determine how socket movement affects the limb health measurements
- The study prosthetist will set vacuum level set to first level
- Digital Image

2. Study Visit 2, 3, 4 (month 1, 2, 3) Subjects will return at 1, 2, and 3 months after study visit 1 where the following research activities will take place:

- Subject will perform seated tasks, standing tasks, and walking on a treadmill task. Skin health measurements will be taken before and after the activity period.
- Hyperspectral Imaging
- Hitachi Aloka Ultrasound
- Skin Temperature
- Surface Electrical Capacitance
- TEWL measurement
- Transcutaneous Oxygen Measurement
- This data will be used to determine how socket movement affects the limb health measurements
- The study prosthetist will set the vacuum level set to the next treatment level except at study visit 4.
- At the end of visit 4, patients will be returned to their standard of care prosthesis. The study prosthetist will be available to review and adjust the fit of their existing prosthesis.
- Digital Image

VIII. Aim 3 (n=30 will be performed at IU under current approved protocol):

Rationale for the amendment: As per the approved DoD proposal, n=60 (n=30 each at IU and Willow wood for Limb Heath analysis, current approved IU IRB protocol) and n=60 subjects were supposed to be completed at Walter Reed (WR) for Functional analysis. We have received a request from WR to perform Functional analysis on the remaining subject that will be enrolled for limb health analysis (this is due to COVID-19 and availability of subjects at WR. The request from WR was also in view of short time line remaining (study end date 09/2021).

After receiving consent, the first enrollment visit will be scheduled for the subjects to see the IU study prosthetist to initiate the “test” socket fitting visits.

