***Note* Study Visit #2A and #2B can be combined and performed in a single study visit upon the discretion of the subject.**

Subjects will begin in their current standard of care prosthesis (the prosthesis worn at time of study enrollment), wherein the following research activities will take place in the following order:

- Subjective questionnaires [Veterans RAND 36-Item Health Survey (VR
- 36, PEQ, Socket Comfort Scores (SCS), and National Institute of Health (NIH) Patient-Reported
- Outcomes Measurement Information System (PROMIS)
- Functional evaluation [Comprehensive High-level Activity Mobility Predictor (CHAMP)]
- Biomechanical evaluation of gait during 6min walking test
 - a. Positioning markers will be placed on the subject while performing the walking assessment to track and describe the movement of the body in three dimensions.
- Repeat SCS outcome

**** applicable to any new enrollments and/or any already enrolled subject completed their limb health part (16 weeks in test sockets followed by 4 weeks in SoC socket as wash off period)**

Following completion of these activities in study visit 2A & B, the subjects will be fitted with the adaptive vacuum suspension by a certified prosthetist that they will wear subsequently wear the device for 16 weeks

The study team will follow up subjects with a weekly phone call to determine the compliance for the use of research socket.

C. **Study Visit #3A – Final Visit (Week 16, +/-2 weeks).** After 16 weeks of wearing the “research” socket the following research activities will take place in the following order:

- Subjects will be asked to walk on a treadmill for 10 mins. The following residual and sound limb health measurements will be taken before and after the activity period with the exception of conducting post-activity ultrasound and digital imaging, is as follows
 - Surface Electrical Capacitance
 - TEWL measurement
 - Hyperspectral Imaging
 - Ultrasound (pre-activity only)
 - Perfusion/ Blood flow
 - Digital Image (pre-activity only)

C.i **Study Visit #3B**— the visit will take place either the same day of Visit 3A or another day within the Week 16, +/-2 weeks based on subject convenience, to repeat research activities previously performed in study visit # 2A

- Subjective questionnaires [Veterans RAND 36-Item Health Survey (VR 36, PEQ, Socket Comfort Scores (SCS), and National Institute of Health (NIH) Patient-Reported Outcomes Measurement Information System (PROMIS)]

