All subjects will be compensated \$100 for each of the completed visits. Aim 1 subjects will be compensated \$100 for the completed study visit 1. Aim 2 subjects will have 4 total visits and will be eligible for a maximum of \$400 for completion of all study visits. Aim 3 subjects will have 3 total visits and will be eligible for a maximum of \$450 for the completion of all visits per following schedule: Visit #1 (\$50), Visit #2A & B (\$150, for completing all socket fitting activities

& baseline) and Visit #3A&B (\$250). Subjects will not be paid if any of study visits are not completed.

XV. Statistical Analysis:

Patient demographics and clinical characteristics will be described using frequencies and percentages for categorical data and median and the interquartile range (IQR) for continuous data. In Aim 1, random-effects linear regression will be used to assess the relationship between wave amplitude and distal movement (or lateral shift) controlling for vacuum pressure. Patient ID will be the random-term in the model. In Aim 2, random-effects linear regression will also be used to compare percent change in limb perfusion across adaptive EVS and suction at 12 weeks controlling vacuum pressure and controlling for the baseline EVS and suction values. In Aim 3, a random-effects linear regression model will be used to establish the relationship in amputee performance (as measured by the CHAMP tasks) and residual limb health across EVS and suction and across EVS and pin-locking/lanyard in a cross-over design. The model includes terms for group (EVS vs. suction or EVS vs. pin-locking/lanyard), sequence (EVS to suction vs. suction to EVS or EVS to pin-locking/lanyard vs. pin-locking/lanyard to EVS), and visit (second vs. first). All statistical models will account for the effect of age, diabetes status and smoking history by including them as the covariates in the models. As per need, subjects may be stratified based upon diabetes status and arterial blood flow status. The *p*-values produced in the study will be adjusted using the Holms procedure to control the overall type I error at 0.05 due to the multiple comparisons. All analyses will be run using Stata 13.1, Stata Corporation, College Station, Texas.

XVI. References:

1. Lake, C. The evolution of upper limb prosthetic socket design. *Journal of Prosthetics and Orthotics* 20, 85 (2008).

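### The Aim 3 cross-over model needs both device orders, but the only Aim 3 schedule given measures function in one order, so device and time cannot be separated

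*Combined protocol and SAP*

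**What the plan says.** Section XV applies a random-effects linear regression to CHAMP performance and residual limb health in Aim 3 and calls the design a cross-over. "The model includes terms for group (EVS vs. suction or EVS vs. pin-locking/lanyard), sequence (EVS to suction vs. suction to EVS" and the matching pin-locking/lanyard orders are named, followed by a visit term (second against first). Age, diabetes status and smoking history are covariates.

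Section VIII gives the only detailed Aim 3 schedule, and its heading ties it to one site: "Aim 3 (n=30 will be performed at IU under current approved protocol". At Visit 2B, "Subjects will begin in their current standard of care prosthesis (the prosthesis worn at time of study enrollment"), and complete the questionnaires, CHAMP and the gait test. They then wear the adaptive vacuum system for 16 weeks. The same functional assessments are listed again at Visit 3B: "the visit will take place either the same day of Visit 3A or another day within the Week 16, +/-2 weeks". Afterwards subjects choose which socket to keep; no further assigned period is described. A footnote extends Visit 2B to subjects who have already finished the limb-health part: "16 weeks in test sockets followed by 4 weeks in SoC socket as wash off period".

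Section V outlines Aim 3 for all 120 subjects "with a total of 3 visits at 0 week (baseline), 0-4 weeks (socket fitting visits), and 16 weeks (final visit"). It also says "Aim 3 studies performed at IU, OWW and WRNMMC per their approved IRB protocols" and "Subjects enrolled in Aim 2 can participate in Aim 3". The OWW and WRNMMC protocols are not part of the supplied text.

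**The concern.** A model with group, sequence and visit terms separates device from time only if some subjects are measured in each order. Section VIII describes one order, and no supplied text describes randomisation or other assignment to a sequence. If every subject on that schedule is measured first in standard of care and then in the test socket, the model cannot be fitted as written. Software would drop the redundant terms and leave a single coefficient that mixes device effect with CHAMP practice and anything else that changes over the interval. Section XV would still describe that coefficient as coming from a model with sequence and visit terms. Since Section II states the Aim 3 objective as comparing the adaptive vacuum system with standard of care, the main Aim 3 conclusion for these subjects is affected.

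There are two related gaps. The model has no term for earlier exposure to the vacuum socket, which the already-enrolled subjects have, as does any Aim 2 subject who enters Aim 3. For limb health, it is unclear whether a standard-of-care measurement exists at all.

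**Working it through.** The plan gives no power calculation, SD or effect size for Aim 3, so there is no figure to reproduce. The check is structural, followed by illustrations on stated assumptions.

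**1. Rank of the model.** Code each observation as intercept, group (EVS = 1), sequence (EVS first = 1) and visit (second = 1).

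- Section VIII subject: Visit 2B is (1, 0, 0, 0) and Visit 3B is (1, 1, 0, 1). The sequence column is zero throughout and the group and visit columns are identical.
- A subject in the reverse order would add (1, 1, 1, 0) and (1, 0, 1, 1).

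| Data | Rank, 4 terms | Rank with age, diabetes, smoking (7 terms) |
|---|---|---|
| One order, n=30 | 2 | 5 |
| One order, n=120 | 2 | 5 |
| Both orders, 15 + 15 | 4 | 7 |

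More subjects do not help. A 15/15 mix of suction and pin-locking users leaves the rank at 2 of 4 when the comparator is coded as one binary group.

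**2. The wash-off footnote.** Those subjects wore the test socket earlier, but their first functional measurement is still Visit 2B in standard of care and their second is Visit 3B. They supply no EVS-first functional measurement, only a previously exposed baseline.

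**3. What the surviving coefficient contains.** Its expectation is device effect + drift. With no device effect, the paired test has standardised shift dz = drift / sqrt(2(1 − rho)), noncentrality dz × sqrt(n) and n − 1 degrees of freedom. Example: drift 0.2 SD and rho 0.5 give dz = 0.2 / sqrt(1) = 0.2, noncentrality 0.2 × sqrt(30) = 1.10, and 18.5% rejections at two-sided 0.05. Drift and rho are assumed; the documents give neither.

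| Drift (SD) | n=30; rho 0.3 / 0.5 / 0.7 | n=15; rho 0.3 / 0.5 / 0.7 |
|---|---|---|
| 0.05 | 5.6 / 5.8 / 6.4% | not tabulated |
| 0.1 | 7.3 / 8.3 / 10.5% | 6.1 / 6.5 / 7.5% |
| 0.2 | 14.6 / 18.5 / 27.7% | 9.4 / 11.2 / 15.4% |
| 0.3 | 26.9 / 35.5 / 53.6% | 15.0 / 19.2 / 28.7% |

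The n=15 column applies if the 30 split evenly into suction and pin-locking users and are modelled separately (an assumption). A simulation of 200,000 runs at n=30 and rho 0.5 gave 8.3% at 0.1 SD and 18.7% at 0.2 SD.

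**4. Pooling with another site.** Suppose another site measured 60 subjects in both orders, 30/30 (hypothetical), and one shared visit term is used. The device estimate is (mean change in standard-of-care-first subjects − mean change in EVS-first subjects) / 2. If the visit effect at IU differs by d, the standard-of-care-first mean moves by 30d/60 = d/2, so the device estimate moves by (d/2 − 0)/2 = 0.25d. The pooled model can be estimated, but only by assuming a visit effect common to all sites.

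**5. Limb health timing.** Three statements do not agree:

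- Section V puts baseline at week 0.
- Section VIII, under the socket fitting visits, starts the 16 weeks of test-socket wear once the fit is comfortable, which is before Visit 2A.
- Section VIII, after Visit 2B, places fitting with the adaptive vacuum suspension after Visits 2A and 2B.

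None of them says which socket is worn at Visit 2A.

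**The case against.** The strongest reply is about scope. Section XV covers Aim 3 as a whole. Section VIII explains that functional analysis was first planned for 60 subjects at WRNMMC and extended to the limb-health cohort by amendment. WRNMMC and OWW follow their own protocols, and either may assign both orders. The Section V visit outline names no device, so it is weak evidence on order. This stands as a limit: what is shown is that the model does not fit the Section VIII schedule, not that it fails at every site.

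Smaller points:

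- **Sample size.** Thirty is an upper limit for functional data at IU. At an assumed n=20, a 0.2 SD drift gives 11% to 20%.
- **Holm adjustment.** At an assumed first step of 0.05/4 = 0.0125, n=30 and 0.2 SD drift give 5% to 12% per test. That is lower than the unadjusted figures but still well above 1.25%.
- **Comparator-specific coding.** Separate group and sequence terms for suction and pin-locking raise the rank to 4 of 5. Neither device effect can be separated from visit even then.
- **Socket at Visit 3B.** It is not named, and the text says it repeats Visit 2A while listing the Visit 2B activities. The test socket is the natural reading, since Visit 3A follows 16 weeks in it and Section XII treats use of another socket as non-compliance.
- **Prior exposure.** Section V says the vacuum suspension is new to all enrolled subjects. That is compatible with exposure gained during Aim 2, where Section VII has the prosthetist setting vacuum levels. The number of Aim 2 subjects who enter Aim 3 is not given.
- **Severity.** The fix leaves the confounding in place, so one could call it a matter of description. But a stated model that cannot be fitted to the documented schedule has to be replaced.

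**Conclusion.** The concern holds, and the plan must be corrected. For subjects on the Section VIII schedule (at most 30 at IU, plus OWW if it follows the same schedule), the stated model has rank 2 of 4, and device is fully confounded with time for CHAMP, questionnaires and gait. This rests only on the written visit order and on the test socket being worn at Visit 3B; it needs no numerical assumption. The rejection rates are illustrations whose size depends on assumed drift and correlation: slight inflation at 0.05 SD (about 6%), 27% to 54% at 0.3 SD. A group, sequence and visit model can be estimated only for a comparator measured in both orders at some site, or by assuming a visit effect shared across comparators and sites. Nothing supplied shows the reverse order, and nothing supplied rules it out at OWW or WRNMMC.

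**What to change.** 1. For subjects on the Section VIII schedule, remove the cross-over description, the sequence term and the separate visit term. Fit one within-subject contrast with a patient random intercept, and report it as a before-after change in which device and time are confounded.
2. For previously exposed subjects (already-enrolled Aim 3 subjects and any from Aim 2), add a prior-exposure indicator and its interaction with the contrast, or run a sensitivity analysis without them. The interaction model has full rank, 4 of 4, but will be imprecise with so few subjects.
3. State the measured order at OWW and WRNMMC. Keep the cross-over model only for data from a protocol that assigns both orders. If sites are pooled, state the shared-visit-effect assumption.
4. Reconcile Section V with the two statements in Section VIII on when test-socket wear starts, and state which socket is worn at Visit 2A. If it is the test socket, make no EVS against standard-of-care limb-health claim from these subjects.

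The cost is SAP wording, a simpler model on the same data and one statement of order per site. The functional claim for these subjects weakens to change from standard of care. Excluding a share f of subjects multiplies the standard error by 1/sqrt(1 − f): 1.15 at f = 0.25 and 1.41 at f = 0.5 (shares assumed; the documents give none).
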